Assessment; IWRS = interactive web response system; OLE = open-label extension; PK = pharmacokinetic; WOCBP = women of childbearing potential; VIIS = Visual Index for Ichthyosis Severity

- a. Upon signing informed consent and entering the Screening Period, subjects will stop using physical and medical treatments for LI, including balneotherapy, and begin to washout prohibited topical and systemic treatments with designated washout periods, as applicable. Before asking a subject to enter washout, investigators should confirm the subject meets study eligibility criteria, except for LI severity (Inclusion Criterion #3). Washout may be up to 90 days. After completing any necessary Washout Period, subjects must return to the site within 35 days before the Baseline Visit within the 97-day Screening Period to have their LI severity assessed and study eligibility requirements determined. During washout, subjects may continue their standard of care of visible skin (face and scalp) for cosmetic reasons and of extremities (palms/soles) to avoid functional consequences on walking or moving their fingers. In the US/EU, this may include compounded emollients with keratolytics (alpha or beta hydroxyl acids) and/or urea. The investigator should approve and document these standard of care treatments in the electronic case report form (eCRF). If the standard of care treatments of the face and/or palms/soles contain prohibited medications, they must be stopped at the Baseline Visit. Subjects may shower, but not bathe or swim during the Screening Period.
- b. Day 90 procedures should be conducted for subjects who terminate the study early. If a subject discontinues IP, but continues to attend clinic visits, Day 90 will occur as scheduled. Day 90 will be the first visit of the OLE for subjects who choose to continue. Subjects who decide to continue into the OLE will have the following additional procedures: 1) sign informed consent; 2) will be weighed; 3) will be instructed on study drug application; 4) will be given new diaries, and 5) will be provided with study drug.
- c. A Follow-up telephone call will be made within 14 days after Day 90 to subjects who choose not to continue into the OLE to assess any ongoing adverse events.

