10.2.3 Follow-up Telephone Call (± 14 days after Day 90) – Only Subjects Who Do Not Continue into Open-label Extension

Clinic staff will telephone subjects who choose not to continue into the Open-label Extension within 14 days after Day 90 to assess any ongoing AEs.

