10.2.4.6 Visit 10 (Day 180 ±7 days) or Early Termination

The following procedures will be performed at this study clinic visit:

1. Perform a physical examination.
2. Record vital signs (blood pressure and pulse).
3. Record concomitant medications and concomitant therapies.
4. Record IGA.
5. Record VIIS.
6. Assess roughness.

7. Record palm/sole assessment.
8. Record palm/sole assessment of fissuring.
9. Record ectropion score.
10. Assess local tolerance
11. Record AEs and review diary.
12. Perform a 12-lead ECG.
13. Perform a urine pregnancy test for WOCBP.
14. Collect blood and urine for routine laboratory tests (subject must be fasting at least 8 hours) and coagulation panel.
15. Collect a PK blood sample (all subjects)
16. Collect returned study drug tubes; confirm study drug compliance by weighing returned kits (tubes and boxes, but not leaflets) and reviewing diaries.

10.2.4.7 Follow-up Evaluation – Open-Label Extension (Day 194 or 14 days after End of Open label Treatment/Visit 11)

At 14 days after the last administration of the IP, the following procedures will be performed:

1. Perform a limited physical examination.
2. Record vital signs (blood pressure and pulse).
3. Record any concomitant medications/therapies.
4. Record IGA.
5. Record VIIS.
6. Assess roughness.
7. Record palm/sole assessment.
8. Record palm/sole assessment of fissuring.
9. Record ectropion score.
10. Assess and record AEs occurring since the last evaluation and review diary.
11. Perform a urine pregnancy test for WOCBP.

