11.1.6 Treatment-Emergent Adverse Events

An AE is defined as treatment emergent if the first onset or worsening is after the first application of IP (trifarotene or vehicle) and not more than 14 days after the last application of IP.

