11.2. Event Assessment and Follow-up of Adverse Events

The occurrence of an AE or SAE may come to the attention of study personnel during study visits and interviews of a study participant presenting for medical care or upon review by a study monitor.

All reported AEs, including local and systemic AEs not meeting the criteria for SAEs, will be captured on the appropriate eCRF. Information to be collected includes event description, time of onset, clinician's assessment of severity, relationship to study product (assessed only by those with the training and authority to make a diagnosis), and time of resolution/stabilization of the event. All reported AEs occurring while on study must be documented appropriately regardless of relationship. All reported AEs will be followed to adequate resolution.

Any medical condition that is present at the time that the participant is screened will be considered as baseline and not reported as an AE. However, if the study participant's condition deteriorates at any time during the study, it will be recorded as an AE.

Changes in the severity of a reported AE will be documented to allow an assessment of the duration of the event at each level of severity to be performed. AEs characterized as intermittent require documentation of onset and duration of each episode.

Study clinic personnel will record all reportable events with start dates occurring any time after informed consent is obtained until 14 (for nonserious AEs) or 30 days (for SAEs) after the last day of study participation. At each study visit, the investigator will inquire about the occurrence of AE/SAEs since the last visit. Events will be followed for outcome information until resolution or stabilization.

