13.1.6.2 Adverse Events

All AEs will be coded using the Medical Dictionary for Regulatory Activities (MedDRA), Version 20.1 or higher.

Treatment-emergent AEs are defined as:

- AEs with onset at the time of or following the start of treatment with IP through the Follow-up Visit or Early Termination Visit, whichever occurs first, or
- AEs starting prior to the start of treatment but increasing in severity or relationship at the time of, or following, the start of treatment with IP through the Follow-up Visit or Early Termination Visit, whichever occurs first.

The number and percentage of subjects with AEs will be displayed by each treatment group in the Double-blind Period and overall in the OLE by system organ class and preferred term. Summaries of AEs by severity and relationship to IP will also be provided. Serious adverse events and AEs resulting in discontinuation of IP will be summarized separately in a similar manner. Subject listings of AEs, SAEs, and AEs causing discontinuation of IP will be produced.

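### Sections 11.1.6 and 13.1.6.2 define the treatment-emergent AE window differently, so TEAE counts for subjects who do not complete the open-label extension can depend on which section is followed

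*Protocol*

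**What the plan says.** Section 11.1.6 calls an AE treatment emergent if its first onset or worsening falls "after the first application of IP (trifarotene or vehicle) and not more than 14 days after the last application of IP". The end of the window is set by dosing.

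Section 13.1.6.2 has two bullets. The first covers "AEs with onset at the time of or following the start of treatment with IP through the Follow-up Visit or Early Termination Visit". The second covers "AEs starting prior to the start of treatment but increasing in severity or relationship". Both end at a visit: "through the Follow-up Visit or Early Termination Visit, whichever occurs first". The section then plans AE tables by arm for the Double-blind Period and overall for the OLE.

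Four other places decide where those end points fall:

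- Section 10.2.4.7 times the OLE Follow-up Visit (Visit 11) by dosing: "At 14 days after the last administration of the IP, the following procedures will be performed".
- Section 10.2.3 gives subjects who do not enter the OLE a call, not a visit: "Clinic staff will telephone subjects who choose not to continue into the Open-label Extension within 14 days after Day 90".
- Section 8.4 asks subjects who stop treatment to come back for ET procedures but sets no interval. Footnote b to Table 2-1 also allows the other course: "If a subject discontinues IP, but continues to attend clinic visits, Day 90 will occur as scheduled".
- Section 11.2 has sites record events "until 14 (for nonserious AEs) or 30 days (for SAEs) after the last day of study participation".

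**The concern.** One definition follows the last dose and the other follows the visit calendar. They agree only if the closing visit happens to fall 14 days after the last application. A programmer building the TEAE tables can satisfy only one of them.

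Read literally, the visit-based rule errs in both directions. It shuts the window soon after an early stop, while recently applied drug could still be responsible. For a subject who stops the drug but stays in the study, it keeps the window open through weeks without exposure. Safety is part of the primary objective (Section 6.1), and application-site events are AEs of special interest (Section 11.3.1), so the TEAE table is a main output of the study.

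The two sections also treat worsening differently, which matters once tables are split by period.

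**Working it through.** The plan states no figure to reproduce, so the check is date arithmetic on the two rules.

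**Rules.** Let L be the day of the last application.
- 11.1.6: end = L + 14.
- 13.1.6.2: end = the earlier of the Follow-up Visit and the ET Visit.
- Difference = (13.1.6.2 end) − (11.1.6 end). Negative means days left out by 13.1.6.2; positive means days added.

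**Inputs.** The 14 days come from 11.1.6. Days 90, 180 and 194 are nominal visit days from Tables 2-1 and 2-2. The call window of 14 days after Day 90 is from 10.2.3. The Day 30 stop, the ET delay of 1, 3 or 7 days and the last application on Day 86 to 89 are my assumptions for illustration.

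| Subject | 11.1.6 end | 13.1.6.2 end | Difference |
|---|---|---|---|
| OLE completer, L = 180, Visit 11 on Day 194 | 180 + 14 = 194 | 194 | 0 |
| Stops Day 30, ET visit 1 day later | 30 + 14 = 44 | 31 | −13 |
| Stops Day 30, ET visit 3 days later | 44 | 33 | −11 |
| Stops Day 30, ET visit 7 days later | 44 | 37 | −7 |
| Stops Day 30, keeps attending, Day 90 visit closes the window | 44 | 90 | +46 |
| Stops Day 30, keeps attending, call on Day 104 closes the window | 44 | 104 | +60 |
| Declines OLE, L = 89, call on Day 91 | 103 | 91 | −12 |
| Declines OLE, L = 86, call on Day 104 | 100 | 104 | +4 |

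**Bound on the loss.** For an ET visit d days after the last application, the loss is 14 − d. The ET visit includes a PK sample, and PK visits must fall at least 24 hours after application (Section 9.2). So d is at least 1 and the loss is at most about 13 days.

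**OLE decliners.** The last two rows assume that the call counts as the Follow-up Visit. If it does not, 13.1.6.2 names no event that closes the window for these subjects.

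**Worsening.** An AE that begins during treatment is already a TEAE by onset under either section, so the narrower worsening rule does not change its overall status. The rule matters for the OLE table. An AE that began on double-blind treatment and worsens on open-label 200 µg/g has neither an onset in the OLE nor, if treatment started at Day 1, an onset before treatment. Separately, an AE from before treatment that changes only in assessed relationship counts under 13.1.6.2 and not under 11.1.6.

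**The case against.** The strongest reply is that this affects few subjects and little information. The windows coincide for OLE completers. The AE that makes someone stop begins before the ET visit, so both definitions count it. Only events that start between the ET visit and 14 days after the last dose are at issue. These leave the TEAE tables but not the record, because the AE and SAE listings in 13.1.6.2 are not confined to TEAEs. The off-drug case is an exception, since 8.4 asks those who stop to return for ET procedures, and that visit would close the window. Safety analyses are descriptive (Section 13.1.6). All of this stands, and it limits the size of the point. It does not remove the conflict, because both definitions are stated in the protocol and a later analysis plan would have to depart from one of them.

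Several stronger readings might be inferred, and the documents do not support them:

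- **That the missing restart at the switch to 200 µg/g makes the tables differ by section.** Neither section restarts, so this is a gap in assigning events to periods and not part of the contradiction. It is detail that an analysis plan could settle, and a per-period reading of 13.1.6.2 is open.
- **That worsening on 200 µg/g disappears.** The AE still counts in the double-blind table and appears in the listings. Section 11.2 requires severity changes to be documented, and local tolerability is summarised by period and visit (13.1.6.1).
- **That the cut-off at ET flatters the active arms.** This is plausible, but the protocol gives no discontinuation rates by arm, and intolerance is met first by reduced frequency or an area-specific pause (9.4).
- **That about 24 subjects are affected (0.20 × 120).** The 20% in 13.2 is a drop-out/nonevaluable allowance, not a count of ET visits; subjects lost to follow-up may have none.
- **That two thirds of OLE entrants change exposure.** This needs equal entry from all three arms, and entry is optional and depends on compliance (10.2.4).

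**Conclusion.** The contradiction is real and in current text. Sections 11.1.6 and 13.1.6.2 give different end dates for early terminators, for subjects who stop the drug but stay in the study, and potentially for those who decline the OLE. On the illustrative Day 30 stop, 13.1.6.2 leaves 7 to 13 post-treatment days out of the TEAE tables, or adds 46 to 60 off-drug days if the subject keeps attending. For OLE decliners the difference ranges from −12 to +4 days if the call counts as the Follow-up Visit, and is undefined if it does not. For OLE completers it is nil when Visit 11 falls on its nominal day.

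These figures rest on the assumed stop, visit and call days. How many subjects fall in each group cannot be derived from the protocol, and neither can any imbalance between arms. The point should be corrected before the tables are built; it does not threaten the design.

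**What to change.** Make 13.1.6.2 use the single dosing-anchored window of 11.1.6 for every subject: onset or worsening from the first application to 14 days after the last, whenever the ET visit occurs, with later events listed separately. The status of the follow-up call then no longer matters. Adopting the 11.1.6 wording also drops the change-in-relationship criterion; if the sponsor wants to keep it, that should be a stated choice in both sections.

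As a secondary clarification, state that the OLE tables count onset or worsening on or after the first open-label application.

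The cost is wording in the protocol and the analysis plan. No new data are needed. Nonserious events are recorded for 14 days after the last day of participation, which cannot precede the last application, so collection always reaches L + 14. Start dates and severity changes are already captured (11.2 and 11.2.3).

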2. PROTOCOL SUMMARY

2.1. Synopsis

PRODUCT NAME/NUMBER	Trifarotene (CD5789) Cream HE1
PROTOCOL NUMBER	18-ICH-001
EUDRACT NUMBER	2018-003272-12
DEVELOPMENT PHASE	2
PROTOCOL TITLE	A Phase 2 Randomized, Multicenter, Double-blind, Vehicle-controlled, 90-Day, Safety, and Efficacy, and Systemic Exposure Study followed by a 90-Day Open-label Extension of Trifarotene (CD5789) Cream HE1 in Subjects with Autosomal Recessive Ichthyosis with Lamellar Scale
INDICATION	Lamellar ichthyosis
OBJECTIVES	
Primary: To compare the safety and efficacy of 2 concentrations of trifarotene cream HE1 versus vehicle in subjects with moderate to severe autosomal recessive ichthyosis with lamellar scale, also known as lamellar ichthyosis (LI) after 90 days of treatment.
 
Secondary:
 
 To assess systemic exposure to trifarotene and its major metabolites after topical application of the investigational product (IP) on up to 90% body surface area (BSA) twice weekly. To assess safety for up to 180 days of dosing with open-label trifarotene cream HE1 200 µg/g.

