6.2. Secondary Objectives

The secondary objectives are as follows:

- To assess systemic exposure to trifarotene and its major metabolites after topical application of the investigational product (IP) on up to 90% BSA twice weekly.
- To assess safety for up to 180 days of dosing with trifarotene cream HE1 200 µg/g.

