9.6. Method of Assigning Subjects to Treatment Groups

In the double-blind, parallel-group, randomized period of the study, subjects who meet study entry criteria will be randomly assigned in a 1:1:1 ratio to trifarotene cream HE1 100 µg/g or 200 µg/g or vehicle cream. The randomization schedule will be computer generated using a permuted block algorithm and will randomly allocate IP to randomization numbers. The randomization numbers will be assigned sequentially through a central interactive web response system (IWRS) as subjects are entered into the study. Study center will not be a blocking factor in the randomization schedule.

Premier Research will prepare the randomization schedule before the start of the study. No one involved in the study performance will have access to the randomization schedule before the official unblinding of treatment assignments. No subject will be randomized into this study more than once.

In the OLE, all subjects will receive trifarotene cream HE1 200 µg/g.

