11.3. Special Considerations

11.3.1 Adverse Events of Special Interest

Since topical retinoids are associated with local application site AEs, particularly when beginning treatment, these events will be followed closely during the study and considered AEs of special interest (AESIs).

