13.2. Sample Size Determination

Accounting for a 20% drop-out/nonevaluable rate, a total sample size of 120 subjects randomized in a 1:1:1 ratio to 2 active trifarotene cream HE1 arms and a vehicle cream arm will provide >80% power to detect a difference between each separate trifarotene cream HE1 arm (32 evaluable subjects) and the vehicle cream arm (32 evaluable subjects) 2-sided Fisher's Exact Test assuming a 70% success rate and a 40% success rate, respectively. This study is not powered to detect a difference between the 2 active arms.

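### The planned open-label extension (OLE) tables of AEs, SAEs and discontinuation AEs pool first and continued exposure to 200 µg/g, so they do not show AE experience over up to 180 days on that dose

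*Protocol*

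**What the plan says.** Section 6.2 gives as a secondary objective: "To assess safety for up to 180 days of dosing with trifarotene cream HE1 200 µg/g". The Synopsis (Section 2.1) words the same objective differently: "To assess safety for up to 180 days of dosing with open-label trifarotene cream HE1 200 µg/g".

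Section 9.6 randomises subjects 1:1:1 to 100 µg/g, 200 µg/g or vehicle. For the extension it then states: "In the OLE, all subjects will receive trifarotene cream HE1 200" µg/g. Section 10.1.1 gives each period 90 days and caps treatment at 180 days for those who continue.

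Section 13.1.6.2 fixes the AE display. The number and percentage of subjects with AEs are to be "displayed by each treatment group in the Double-blind Period and overall in the OLE by system organ class and preferred term". SAEs and AEs that lead to stopping the product follow the same layout in separate tables. The OLE Safety population in Section 13.1.1 is not divided by earlier arm.

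Section 11.3.1 explains why application-site events are of special interest: "Since topical retinoids are associated with local application site AEs, particularly when beginning treatment".

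**The concern.** Only a subject randomised to 200 µg/g can pass 90 days on that dose. In the OLE, a former vehicle subject is starting a retinoid and a former 100 µg/g subject is moving to a higher concentration, while a former 200 µg/g subject is in months four to six. A single OLE column counts all three alike.

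If local events come mainly at the start, the pooled percentage is neither the start-up rate nor the continued-exposure rate. Sections 5.2 and 7.3 say that the OLE will evaluate the long-term safety of the higher dose. A reader may therefore take the pooled column as long-term experience, when most of the subjects in it are new to 200 µg/g. Nor can the double-blind 200 µg/g column be combined with the pooled OLE column to give a 180-day picture, because the two cover different subjects.

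**Working it through.** **Inputs**
- Sample size and loss, Section 13.2: "Accounting for a 20% drop-out/nonevaluable rate, a total sample size of 120 subjects randomized in a 1:1:1 ratio", with 32 evaluable subjects stated per arm.
- Period lengths, Section 10.1.1: 90 days each.
- OLE treatment, Section 9.6: 200 µg/g for everyone.
- AE rates by exposure time: not given in the protocol, so assumed below and shown as a range.

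**The plan's own figure.** 120 / 3 = 40 per arm; 40 × (1 − 0.20) = 32. This reproduces the stated 32, and 3 × 32 = 96 in total.

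**Days on 200 µg/g by the end of the OLE**
- Vehicle, then 200: 0 + 90 = at most 90 days.
- 100, then 200: 0 + 90 = at most 90 days.
- 200, then 200: 90 + 90 = at most 180 days.

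**Make-up of the pooled OLE column.** If all 32 evaluable subjects per arm enter, first exposure is 64 / 96 = 67% and continued exposure is 32 / 96 = 33%.

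If entry differs by arm (assumed rates for vehicle / 100 / 200):
- 90 / 90 / 60%: 28.8 + 28.8 + 19.2 = 76.8; continued share 19.2 / 76.8 = 25%.
- 80 / 90 / 100%: 25.6 + 28.8 + 32 = 86.4; continued share 32 / 86.4 = 37%.

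**What pooling could do to a rate (illustration only).** Let p1 be the rate in the first 90 days of 200 µg/g, taken as the same for both former arms, and p2 the rate in days 91-180. With equal entry, the pooled rate is (64 × p1 + 32 × p2) / 96.
- p1 = 40%, p2 = 10%: (25.6 + 3.2) / 96 = 30%, three times p2.
- p1 = 20%, p2 = 5%: (12.8 + 1.6) / 96 = 15%.
- p1 = 50%, p2 = 20%: (32 + 6.4) / 96 = 40%.
- p1 = p2 = 20%: pooled 20%, no distortion.

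Former 100 µg/g subjects are already used to a retinoid, so their rate may lie between p1 and p2; the pooled figure would then move towards p2.

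**Other safety summaries, by section**
- 13.1.6.1, local tolerability: by period, treatment group and visit.
- 13.1.6.3, laboratory values: by treatment group and time point in each period.
- 13.1.6.4, vital-sign shift tables: by period, treatment group and visit.
- 13.1.6.5, ECG measures: by treatment group and time point in each period.
- 13.1.6.2, AEs, SAEs and discontinuation AEs: by treatment group in the Double-blind Period, one overall column in the OLE.

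So the AE section departs from its neighbours. The neighbours in turn leave open what *treatment group* means once everyone is on 200 µg/g.

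**The case against.** A reader might infer that the 180-day objective goes unanswered altogether, or that no planned table follows the 200 µg/g subjects through Day 180. The documents do not support that. If *treatment group* means the randomised arm, the tolerability, laboratory, vital-sign and ECG summaries do follow them. Local tolerability is the measure closest to the start-up problem, and it is summarised by visit, including Day 104, soon after the OLE begins. That objection stands and limits the point to AEs, SAEs and discontinuation AEs. It does not remove the point: the term is undefined for the OLE, and visit-level scores separate early from late reactions, not first from continued exposure.

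A second objection is that Section 13.1 is a summary, with details to follow in the SAP. Nothing in it forbids more columns, event capture does not stop at Day 90, and subject listings of AEs are planned. All true, so nothing is lost irretrievably. But the protocol is not silent on this display; it specifies an overall column. Disposition (Section 13.1.2.1) and compliance (Section 13.1.3) also contrast a by-arm display with an overall one for the OLE. Listings permit reconstruction afterwards but are not a planned summary.

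It is also tempting to size the problem with zero-event bounds: 1 − 0.05^(1/96) = 3.1% against 1 − 0.05^(1/32) = 8.9% (one-sided, exact). These show only how much less 32 subjects can rule out than 96. They do not measure distortion of a rate, since zero events overall means zero in every subgroup, and re-tabulation adds no subjects.

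Finally, the Synopsis wording might be read as planning 180 days of open-label treatment. Section 10.1.1 gives the OLE 90 days, and Section 6.2 omits the open-label qualifier, so this is an editorial mismatch.

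**Conclusion.** The point holds for the AE, SAE and discontinuation-AE tables. As specified, the OLE column combines subjects in their first 90 days of 200 µg/g with subjects in days 91-180, and no planned table of these events isolates or joins up the experience of those who can reach 180 days.

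With equal OLE entry the continued-exposure group is about one third of the column; the assumed unequal entry patterns give 25% to 37%. The count of 32 of 96 rests on the 20% loss in Section 13.2 and on every evaluable subject entering. Section 10.2.4 makes entry optional and dependent on attendance and compliance as judged by the investigator, so 32 is best read as an upper figure under the plan's assumptions. How far a pooled AE rate would differ from the continued-exposure rate cannot be computed from the protocol, which gives no AE rates.

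Safety is descriptive throughout, so no test is affected. The gap lies between a stated objective and the tables meant to serve it. It is worth closing because closing it is so cheap.

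**What to change.** 1. In Section 13.1.6.2, present OLE AEs, SAEs and AEs leading to discontinuation by randomised arm (vehicle to 200, 100 to 200, 200 to 200) as well as overall.
2. Add a cumulative Day 1-180 AE table for the 200-to-200 group.
3. State that *treatment group* in all OLE safety summaries means the randomised arm.
4. Align the Synopsis objective with Section 6.2 on the open-label qualifier.

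The cost is a few extra tables with small columns, about 32 subjects each at best. No new data, visits or subjects are needed. The small columns will give imprecise rates; the overall column stays alongside for rare events.
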